**Table F-1 Typical Strong Inhibitors of CYP3A4**

Strong Inhibitors of CYP3A4
Boceprevir
Clarithromycin
Conivaptan
Elvitegravir/Ritonavir
Fluconazole
Grapefruit juice a,b
Indinavir
Itraconazole
Ketoconazole
Lopinavir/Ritonavir
Mibefradil
Nelfinavir
Posaconazole
Ritonavir
Saquinavir
Telaprevir
Telithromycin
Tipranavir/Ritonavir
Troleandomycin
Voriconazole

a Super-concentrated grapefruit juice

b During the study, patients should not consume large amounts of grapefruit or lime (or products that include these fruits, such as grapefruit juice and orange jam). No more than one cup (120 mL) of grapefruit juice, half a grapefruit or a spoon full (15 g) of orange jam should be consumed each day.

**Table F-2 Typical Strong Inducers of CYP3A4**

Strong Inducers of CYP3A4
Avasimibe
Carbamazepine
Enzalutamide
Mitotane
Phenobarbital
Phenytoin
Rifabutin

Rifampicin  
Enzalutamide  
St. John's wort

**Table F-3: Typical Substrates of P-gp and BCRP**

Substrates of P-gp	Substrates of BCRP
Aliskiren	Methotrexate
Ambrisentan	Mitoxantrone
Colchicine	Imatinib
Dabigatran etexilate	Irinotecan
Digoxin	Lapatinib
Everolimus	Rosuvastatin
Fexofenadine	Sulfasalazine
Imatinib	Topotecan
Lapatinib	
Maraviroc	
Nilotinib	
Posaconazole	
Ranolazine	
Saxagliptin	
Sirolimus	
Sitagliptin	
Talinolol	
Tolvaptan	
Topotecan	

## Appendix G Guideline to Interpreting the Causality Question

The following factors should be considered when deciding if there is a “reasonable possibility” that an AE may have been caused by the drug.

- Time Course. Exposure to suspect drug. Has the patient actually received the suspect drug? Did the AE occur in a reasonable temporal relationship to the administration of the suspect drug?
- Consistency with known drug profile. Was the AE consistent with the previous knowledge of the suspect drug (pharmacology and toxicology) or drugs of the same pharmacological class? Or could the AE be anticipated from its pharmacological properties?
- Dechallenge experience. Did the AE resolve or improve on stopping or reducing the dose of the suspect drug without treatment of the reported event?
- No alternative cause. The AE cannot be reasonably explained by another etiology, such as the underlying disease, other drugs, other host or environmental factors.
- Rechallenge experience. Did the AE reoccur if the suspected drug was reintroduced after having been stopped? HMPL would not normally recommend or support a rechallenge.
- Laboratory tests. A specific laboratory investigation (if performed) has confirmed the relationship?

A “reasonable possibility” could be considered to exist for an AE where 1 or more of these factors exist.

In contrast, there would not be a “reasonable possibility” of causality if none of the above criteria apply or where there is evidence of exposure and a reasonable time course but any dechallenge (if performed) is negative or ambiguous or there is another more likely cause of the AE.

In difficult cases, other factors could be considered such as:

- Is this a recognized feature of overdose of the drug?
- Is there a known mechanism?

Ambiguous cases should be considered as being a “reasonable possibility” of a causal relationship unless further evidence becomes available to refute this. Causal relationship in cases where the disease under study has deteriorated due to lack of effect should be classified as no reasonable possibility.

## **Appendix H Clinical Evaluation of Possible Drug-Induced Liver Injury (DILI)**

If ALT or AST is elevated to higher than 3 x ULN **and** bilirubin is elevated to higher than 2 X ULN, fruquintinib treatment should be discontinued immediately, and supportive treatment should be given. This combination of lab abnormalities meets the biochemical criteria for Hy's law, which is associated with a markedly increased possibility of severe drug-induced liver injury (DILI), and may progress to liver transplantation or death (FDA Guidance for Industry - Drug-Induced Liver Injury: Premarketing Clinical Evaluation. FDA, 2009).

If the biochemical criteria for Hy's law are met, fruquintinib should be immediately discontinued, and patients need to be very closely monitored (bilirubin, ALP, AST, and ALT measured 2-3 times weekly until the results return to baseline or normal), and other causes of liver injury evaluated (eg, new or worsening hepatobiliary metastases; non-malignant biliary obstruction; viral hepatitis A, B, or C; alcoholic or autoimmune hepatitis; preexisting or acute liver disease; ischemic liver injury; right-sided congestive heart failure; new or worsening liver metastases; or concomitant medication that could cause the observed injury). Consultation with a gastroenterologist or hepatologist should be considered.

If the biochemical criteria for Hy's Law have been met, expedited reporting is required (see Section 7.1.2), before waiting for the evaluation of other causes to be completed.

### **Recommended Data Collection for Suspected DILI**

The investigator is recommended to obtain the following information, so as to further evaluate and follow up and complete the clinical data. Data should be recorded on CRFs where possible, and supplemented by investigator reporting as text in the clinical database:

- Medical history of the patient
  - Detailed history of current symptoms, diagnosis of complications and medical history
  - Previous medical history (viral hepatitis, alcoholic hepatitis, autoimmune disease, biliary tract disease and cardiovascular disease, etc.)
  - History of concomitant medication (including OTC and prescription drugs, herbal medicine and dietary supplements), alcohol consumption, recreational drugs and special diet
  - History of exposure to potentially hepatotoxic chemicals
- Complete the following laboratory tests:
  - Haematology
  - Clinical biochemistry: ALT, AST, bilirubin (including total bilirubin and direct bilirubin), ALP, albumin, prothrombin time or INR, amylase, fasting blood glucose, cholesterol and triglycerides
  - Other Serum Tests: Hepatitis A (Anti-IgM and Anti-IgG), hepatitis B (HbsAg, Anti-HBs and HBV DNA), hepatitis C (Anti-HCV, and HCV RNA test is required for any patient with positive test result), hepatitis D (Anti-IgM and Anti -IgG), hepatitis E (Anti-HEV and Anti-HEV IgM).

- Complete appropriate auxiliary examination:
  - Patients with confirmed elevation of ALT/AST combined with TBili are required to receive abdominal ultrasonography or other clinically applicable imaging examination within 48 hours (to exclude biliary tract, pancreatic, or intrahepatic causes, such as new or worsening hepatobiliary metastases or biliary calculi) and obtain the liver imaging result as soon as possible. If an alternative cause (such as biliary tract, pancreatic, or intrahepatic causes) of abnormal hepatic results cannot be confirmed by imaging, paracentesis is recommended for pathological examination after obtaining consent of the patient;
  - If suspected cardiovascular causes exist, cardiac ultrasonography is recommended to exclude cardiovascular dysfunction (ie, right heart failure);

Long-term follow-up: Perform close monitoring on the patient through repetitive tests of ALT, AST and bilirubin (including total bilirubin and direct bilirubin) two to three times weekly until the laboratory ALT and/or AST abnormality becomes stable or recovers, and then proceed according to the protocol.

[figure not shown]
## **Appendix I Management of Hypertension in Patients Receiving Fruquintinib**

Hypertension is a common AE that has been reported in patients taking angiogenesis inhibitors (Izzedine, et al 2009), including fruquintinib. Grade 3 AEs have been reported in 16% of patients treated with fruquintinib; no Grade 4 events have been reported to date. It appears that hypertension is a class-effect of VEGFR inhibitors (either antibodies or small molecules).

There is no standard therapy for angiogenesis inhibitor-induced hypertension because there have not been any published controlled clinical trials with specific agents. Therefore, one can take an approach based on the clinical characteristics of particular patients. Calcium channel blockers and angiotensin converting enzyme inhibitors (ACEI) are a reasonable first choice in most cases. For patients with proteinuria, chronic renal disease or metabolic disease, an ACE inhibitor or angiotensin II receptor blockers (ARB) may be preferred; for elderly patients, dihydropyridine calcium channel blockers may be preferred. In this appendix is a summary of the most recent American Heart Association (AHA)/American College of Cardiology (ACC) hypertension treatment guidelines. A cardiologist may be consulted if appropriate.

The objective of antihypertensive therapy in general is to control the blood pressure to a target level <140/90 mmHg. For high-risk populations, such as patients with chronic renal disease and/or diabetes, it may be appropriate to aim for a target blood pressure < 130/80 mmHg. On the following two pages, please see a summary of the most recent AHA/ACC hypertension treatment guidelines.

# Controlling Hypertension in Adults

© 2013 The Authors. *Hypertension* is published on behalf of the American Heart Association, Inc., by Wolters Kluwer; the *Journal of the American College of Cardiology* is published on behalf of the American College of Cardiology Foundation by Elsevier Inc. This is an open access article under the terms of the Creative Commons Attribution Non-Commercial-NoDerivs License, which permits use, distribution, and reproduction in any medium, provided that the Contribution is properly cited, the use is non-commercial, and no modifications or adaptations are made.

JN0080 R1/14

## Controlling Hypertension in Adults

The blood pressure (BP) goal for an individual is set by utilizing a combination of factors including scientific evidence, clinical judgment, and patient tolerance. For most people, the goal is <140 and <90; however, lower targets may be appropriate for some populations such as African-Americans, the elderly, or patients with LV hypertrophy, systolic or diastolic LV dysfunction, diabetes mellitus or chronic kidney disease. Lifestyle modifications (LM) should be initiated in all patients with hypertension (HTN) and they should be assessed for target organ damage and existing cardiovascular disease. Self-monitoring is encouraged for most patients throughout their care, and requesting and reviewing readings from home and community settings can help the provider assist the patient in achieving and maintaining good control. For patients with hypertension in combination with certain clinical conditions, specific medications should be considered first-line treatments.

### Suggested Medications for Treatment of Hypertension in Presence of Certain Medical Conditions

- Coronary artery disease/Post MI: **BB, ACEI**
- Systolic heart failure: **ACEI or ARB, BB, ALDO ANTAG, thiazide**
- Diastolic heart failure: **ACEI or ARB, BB, thiazide**
- Diabetes: **ACEI or ARB, thiazide, BB, CCB**
- Kidney disease: **ACEI or ARB**
- Stroke or TIA: **thiazide, ACEI**

### Lifestyle Modifications (LM)

Modification	Recommendation	Approximate SBP Reduction (Range)**
Reduce weight	Maintain normal body weight (body mass index 18.5–24.9 kg/m  )	5–20 mm Hg/10 kg
Adopt DASH** eating plan	Consume a diet rich in fruits, vegetables, and low-fat dairy products with a reduced content of saturated and total fat	8–14 mm Hg
Lower sodium intake 	a. Consume no more than 2,400 mg of sodium/day; b. Further reduction of sodium intake to 1,500 mg/day is desirable since it is associated with even greater reduction in BP; and c. Reduce intake by at least 1,000 mg/day since that will lower BP, even if the desired daily sodium intake is not achieved	2–8 mm Hg
Physical activity	Engage in regular aerobic physical activity such as brisk walking (at least 30 min per day, most days of the week)	4–9 mm Hg
Moderation of alcohol consumption	Limit consumption to no more than 2 drinks (e.g., 24 oz beer, 10 oz wine, or 3 oz 80-proof whiskey) per day in most men, and to no more than 1 drink per day in women and lighter weight persons	2–4 mm Hg

\*DASH, dietary approaches to stop hypertension

\*\* The effects of implementing these modifications are dose and time dependent, and could be greater for some individuals

#### Abbreviations

ACEI, angiotensin-converting-enzyme inhibitor; ALDO ANTAG, aldosterone antagonist; ARB, angiotensin II receptor blocker; BB,  $\beta$ -blocker; BP, blood pressure; CCB, calcium channel blocker; HTN, hypertension; MI, myocardial infarction; SBP, systolic blood pressure; TIA, transient ischemic attack

## Appendix J Clinical Management of Severe or Serious Hemorrhagic Events

If hemorrhagic events are evaluated as severe (CTCAE Grade  $\geq 3$ ) or serious adverse events, fruquintinib treatment should be discontinued or interrupted immediately, and appropriate treatment measures initiated to control bleeding (e.g. transfusion, radiologic, endoscopic, or elective operative intervention as indicated). When the patient is not well enough to tolerate an invasive procedure or operation, best supportive care is given (see Section 5.2.2.1, Table 13, Dose Adjustment for Hemorrhage at any Site). Patients need to be very closely monitored, both clinically (continuously), and by relevant laboratory testing (INR, aPTT, platelet count, hemoglobin) every 2-3 days until the results return to baseline or normal). During the initial assessment, a focused history and physical examination, with collection of vital signs and laboratory evaluation and imaging evaluation should be obtained, aimed at determining the time of onset, location, severity of bleeding, and whether bleeding is ongoing. Clinicians should be mindful of comorbidities and concomitant treatments (eg. anti-platelet therapy and/or thrombocytopenia, or liver disease) that could also contribute to bleeding and manage them as appropriate. Consultation with other department clinicians should be considered when necessary.

The investigator should closely monitor patients receiving anti-platelet and/or anti-thrombotic drugs during study drug treatment and make a timely decision on whether to continue or stop such drugs in patients that report Grade  $\geq 2$  hemorrhagic events at any site, based on an individual assessment of the risk-benefit balance.

If a hemorrhagic event is evaluated as a severe (CTCAE Grade  $\geq 3$ ) or serious adverse event after taking fruquintinib, the investigator is required to report the event in an expedited fashion (within 24 hours of first awareness) to sponsor (see Table 12 and Section 7.2 Expedited Reporting Requirements).

See the **Management Flowchart** below for guidance on the management of severe or serious hemorrhage at any site.

[figure not shown]

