## 5.2 Dose Modification

### 5.2.1 General Dose Adjustment Note

The severity of AEs will be graded according to the NCI CTCAE v4.03. Reasons for dose modifications or delays, the supportive measures taken, and the outcome will be documented in the patient's chart and recorded in the CRF.

- Any toxicity that meets the definition of DLT during the DLT observation period will be considered as DLT for purposes of dose escalation and MTD determination.
- For any concomitant conditions already apparent at baseline, the dose modifications will apply according to the corresponding shift in toxicity grade, if the investigator feels it is appropriate. For example, if a patient has Grade 1 asthenia at baseline that increases to Grade 2 during treatment, this will be considered a shift of one grade and treated as Grade 1 toxicity for dose-modification purposes.
- For toxicities that are considered by the investigator to be unlikely to develop into serious or life-threatening events, treatment will be continued at the same dose. In addition, no dose reductions or interruptions will be required for anemia (non-hemolytic) because it can be satisfactorily managed, unless serious (Grade  $\geq 3$ ) hemorrhage is present.
- To recover from acute toxicity, unless otherwise indicated, the treatment can be interrupted for up to 14 days. If a treatment delay longer than 14 days is required, the patient should be discontinued from the study drug. Continuation/resumption of fruquintinib treatment after an interruption of more than 14 days must be discussed with the medical monitor or his or her designee.
- Where several toxicities with different grades or severity occur at the same time, the dose modifications should be according to the highest grade observed.

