**Table 13 Dose Adjustment for Hemorrhage at any Site**

AE Grading	Dose Adjustment	Treatment Suggestions
Grade 1	None	Perform follow up visit as scheduled.
Grade 2	The drug can be interrupted and then reduced to the lower dose level should the AE recovered to Grade 1 or baseline level within 14 days.	Provide Active treatment b
Grade 3 or abovea	The study drug should be terminated permanently.	Emergent medical intervention b

a Refer to [Appendix J](#) for clinical management of severe or serious hemorrhage.

b The investigator should closely monitor patients receiving anti-platelet and/or anti-thrombotic drugs during study drug treatment and make a timely decision on whether to continue or stop such drugs in patients that report Grade ≥2 hemorrhagic events at any site, based on an individual assessment of the risk-benefit balance (See Section 5.3.1 Concomitant therapies).

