### 7.1.3.3 Severe Hemorrhagic Events

When a hemorrhagic event meets NCI CTCAE  $\geq$  Grade 3 severity (regardless of whether it is serious or non-serious), the event should be reported to the sponsor no more than 24 hours after first awareness of the event.

The management of severe or serious hemorrhagic events will be conducted according to [Appendix J](#).

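### For Grade 3 or higher hemorrhage, Table 13 gives only permanent termination of study drug, while Appendix J also offers interruption and does not limit that option to serious events below Grade 3

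*Protocol*

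**What the plan says.** Protocol Table 13 sets the dose action for hemorrhage by grade alone. Grade 1 calls for no change. At Grade 2, "The drug can be interrupted and then reduced to the lower dose level should the AE recovered to Grade 1 or baseline level", with a 14-day limit on recovery. At Grade 3 or above, "The study drug should be terminated permanently". A footnote on that last row refers the reader to Appendix J "for clinical management of severe or serious hemorrhage".

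Appendix J opens with events rated severe (Grade 3 or higher) or serious, for which "fruquintinib treatment should be discontinued or interrupted immediately". It then describes measures to control bleeding and supportive care for patients who cannot tolerate a procedure. After the supportive-care sentence it points back: "see Section 5.2.2.1, Table 13, Dose Adjustment for Hemorrhage at any Site". It ends by directing the reader to a management flow chart.

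Protocol Section 7.1.3.3 adds: "The management of severe or serious hemorrhagic events will be conducted according to" Appendix J.

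On the analysis side, SAP Section 17.2.2 identifies events leading to interruption or reduction from the recorded action taken (Drug Interrupted or Dose Reduced). SAP Section 17.2.3 identifies events leading to discontinuation from the response Drug Withdrawal.

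**The concern.** Every hemorrhage of Grade 3 or above falls under both the bottom row of Table 13 and the opening sentence of Appendix J. The first allows one action; the second allows two. Each text refers to the other, and neither says how the two actions are to be divided.

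The main stake is patient safety. Hemorrhage is an identified risk of the drug, and the protocol treats severe bleeding as important enough to require reporting within 24 hours whether or not it is serious. About 12 sites are planned, and two investigators who each follow the protocol in good faith could act differently on the same bleed.

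The second stake is interpretation. The SAP classifies events by the action recorded, so a split between interruption and withdrawal could partly reflect which passage a site read.

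**Working it through.** No arithmetic applies. The check sets the current texts side by side by type of event, then looks for any passage that resolves the difference.

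| Hemorrhage | Table 13 | Appendix J |
|---|---|---|
| Grade 1 or 2, not serious | no change (Grade 1); interrupt, then reduce on timely recovery (Grade 2) | not covered |
| Grade 1 or 2, serious | same rows, because Table 13 does not use seriousness | discontinue or interrupt |
| Grade 3 or above, serious or not | permanent termination only | discontinue or interrupt |

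1. **The two texts cover different sets of events.** Seriousness under Section 7.1.3.1 is separate from grade; for example, inpatient hospitalization is enough. A Grade 2 bleed can therefore be serious, and Appendix J reaches further than the Table 13 row.

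2. **They overlap at Grade 3 and above, and differ there.** The third row of the comparison is the conflict. Table 13 confines interruption to Grade 2; Appendix J offers it without reference to grade.

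3. **Cross-references.** The Table 13 footnote sends severe events to Appendix J, and so does Section 7.1.3.3. The pointer from Appendix J back to Table 13 is attached to the supportive-care sentence and gives neither text priority.

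4. **General rules.** Section 5.2.2.1 takes hemorrhage out of the general toxicity rule in Table 8, so Table 8 cannot settle the matter. Section 5.2.1 says "no dose reductions or interruptions will be required for anemia (non-hemolytic") and makes an exception when Grade 3 or higher hemorrhage is present. Its subject is anemia, so it neither authorizes nor forbids interruption for the bleed itself.

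5. **Comparison within the protocol.** For liver events meeting the biochemical criteria for Hy's Law, Table 14, Section 7.1.3.2 and Appendix H all call for immediate termination or discontinuation and none offers interruption. The looser wording is therefore not how the protocol usually pairs a table with its appendix.

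6. **Effect on the outputs.** A Grade 3 bleed recorded as Drug Interrupted is counted under SAP Section 17.2.2; the same bleed recorded as Drug Withdrawal is counted under Section 17.2.3. The interruption counts in SAP Section 15.1 change with it. The PFS rules in SAP Section 16.1.5 do not use stopping of study drug as an event or a censoring reason, so the definition of the primary endpoint is not directly touched.

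**The case against.** The strongest reply is that the texts can be read as consistent. There are three parts to it.

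- **A combined population.** Appendix J addresses severe and serious events together. Offering both actions is natural wording for a group whose members fall in different rows of Table 13, and Appendix J cites that table. On this reading interruption belongs to the serious lower-grade events.
- **Different moments.** Appendix J says what to do at once, while bleeding is being controlled and assessed; Table 13 gives the lasting decision. Holding the drug and then terminating it would satisfy both. Appendix J contains no rule for resuming drug after a severe bleed.
- **The flow chart.** The figure that Appendix J offers as guidance is not visible in the text available for review, and it may make the split explicit. Its absence here is not a fault of the plan.

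All three are plausible, and they rule out the stronger inference that the protocol knowingly sets two incompatible rules for an identical set of events. What they do not do is supply the missing words. The sentence divides its two actions neither by grade nor by stage of management. A clear flow chart would show the intent, but the written sentence would still need to be aligned with it.

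A reader might also take the 40.7% for hemorrhages in Table 3 of the protocol as the size of the problem. It is not a Grade 3 or higher rate: the terms that the table lists as most frequent are occult blood, blood in the urine and epistaxis. Nor does the planned total of 128 patients measure it, since only patients with a severe bleed are affected.

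**Conclusion.** The inconsistency holds for Grade 3 or higher hemorrhage, as a matter of written text. Table 13 states permanent termination only; Appendix J, to which Section 7.1.3.3 assigns management of these events, also allows interruption and does not reserve it for serious events below Grade 3.

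Its size cannot be stated. The documents give no rate of Grade 3 or higher hemorrhage, and the number of patients affected may be small. The data consequence is confined to descriptive action-taken and exposure tables. SAP Section 5.5 plans no hypothesis tests, and the 24-hour reporting duty is the same whichever action is taken. The reason to act is consistent handling of a severe safety event, not a threat to the efficacy conclusions.

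The conclusion rests on the current written text and on the flow chart being unseen. A chart that reserves interruption for lower-grade events would narrow the point to aligning one sentence. Nothing here implies a view on which action is clinically right.

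**What to change.** Reconcile Table 13, the opening sentence of Appendix J and the Appendix J flow chart so that each combination of grade and seriousness has one stated action. If an immediate step and a lasting decision are both intended, the text should name them as such. State in Section 7.1.3.3 or in Appendix J which passage governs. The clinical team must decide the actions.

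Two references in Appendix J can be corrected in the same edit. It places Table 13 in Section 5.2.2.1, although Section 5.2.2.2 introduces it, and its expedited-reporting sentence cites Table 12, which concerns platelet counts.

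For patients already treated under the present wording, a short listing of Grade 3 or higher hemorrhages with the recorded action would let a reader see whether handling varied. The cost is a wording change in the protocol, a check of the flow chart, a memo to sites and, if wanted, that one listing. No analysis method or sample size changes.
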